Young, healthy, myopic adults with no history of long-term contact lens wear and ocular disease were recruited. Subjects who occasionally wear soft lenses (such as for sports) were eligible. The inclusion criteria included myopia between -4.00D and -5.00D sphere, and with-the-rule astigmatism (axis 180 ± 30) of not more than 1.50D, where the spherical equivalent was between -4.00D to -5.75D. The difference in myopia between the two eyes was within 1D for both the sphere and cylinder components. The inclusion criterion in refractive error for this study is to eliminate the confounding factor for orthokeratology caused by a wide refractive range. The best-corrected visual acuity was at least 0.10 logMAR in each eye when measured using the Early Treatment Diabetic Retinopathy Study (ETDRS) charts (Prevision Vision, La Salle, IL) under a normal room lighting condition.

Procedures

The following baseline data were collected: non-cycloplegic manifest refraction, ocular biometry through partial coherence interferometry (Zeiss IOLMaster; Zeiss Humphrey, Dublin, CA), corneal topography (Medmont E300, Medmont Pty Ltd., Vermont, VIC, Australia), corneal thickness through swept-source optical coherence tomography (Casia SS-1000, Tomey, Nagoya, Japan), and corneal biomechanics using an Ocular Response Analyzer (ORA; Reichert Inc., USA).

Five valid axial length measurements were captured using the IOLMaster, and an average reading was generated for analysis. In corneal topography, three images (scores higher than 95) were automatically captured. The mean value of the simulated steepest and flattest keratometry readings was used for analysis. Corneal thickness was measured using a "3D Corneal Map" scan by the swept-source optical coherence tomography. Three automated measurements were obtained for each scan while the subject focused on a central target inside the instrument. In ORA, three acquisitions were obtained each with a waveform score of at least 6.0. Corneal hysteresis (CH), corneal resistance factor (CRF), and corneal-compensated intraocular pressure (IOPcc) were measured.

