Ethics clearance was obtained from the institutional review board of The Hong Kong Polytechnic University. Informed consent was obtained from all participants included in the study. This study was registered at ClinicalTrials.gov (NCT02719535, registered March 25, 2016) and in the University of Hong Kong HKU Clinical Trials Register (HKUCTR-1957, registered Feb 1, 2016).

Analysis of data

The corneal parameters and refractive error obtained in each aftercare visit were compared with the baseline data. Data of one eye of each subject who completed the 6-month orthokeratology were analyzed, with the eye with residual sphere closer to plano at the 6-month visit being selected. If the residual sphere was the same in both eyes, then the eye with less residual astigmatism was selected. For subjects with the same residual refractive errors in both eyes, the right eye was selected. Normality was checked using the Shapiro-Wilks test. Repeated-measure analysis of variance or the Friedman test were used to compare changes in ocular parameters throughout the study, that is, from baseline to the end of the 6-month orthokeratology. Baseline ocular parameters that could best predict myopia reduction were identified through linear regression (Pearson or Spearman). Reduction of sphere at the 6-month visit was used as the dependent outcome response, and the various baseline ocular parameters were treated as independent predictors. All data analysis and graphical presentation were completed using SigmaPlot 13 (Systat Software, Inc.).

(d) References

- 3. Pärssinen O. The increased prevalence of myopia in Finland. Acta Ophthalmol. 2012;90: 497-502.

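### The analysed eye is chosen by its own 6-month residual sphere, a component of the Objective 2 outcome, so predictor associations can be distorted; for biomechanics the main risk is a weakened slope and lost power

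*Combined protocol and SAP*

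**What the plan says.** The rule is in section (c) Methods, Analysis of data. Among subjects who complete 6 months, one eye is analysed, "with the eye with residual sphere closer to plano at the 6-month visit being selected". Ties go to a second post-treatment value: "If the residual sphere was the same in both eyes, then the eye with less residual astigmatism was selected". Only then does a neutral rule apply: "For subjects with the same residual refractive errors in both eyes, the right eye was selected".

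The same paragraph defines the prediction analysis: "Reduction of sphere at the 6-month visit was used as the dependent outcome response", with unlisted baseline ocular parameters as predictors, examined by linear regression (Pearson or Spearman). It names no other outcome for prediction, so this is taken as the analysis for Objective 2 in section (b), which asks whether corneal biomechanics predicts the rate of orthokeratology.

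Under Subjects, fellow eyes may differ at baseline: "The difference in myopia between the two eyes was within 1D for both the sphere and cylinder components". Under Procedures, refraction is among the baseline measurements: "The following baseline data were collected: non-cycloplegic manifest refraction". The plan describes no fixed-eye, random-eye, both-eye or sensitivity analysis.

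**The concern.** Analysing one eye per subject avoids clustering, but the choice of eye should not depend on the outcome. Here it depends on the 6-month residual, which is one of the two terms that make up the outcome. In each subject the less well corrected eye is set aside.

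Section (a) motivates the study by patients in whom orthokeratology is slow or ineffective, and asks whether biomechanics could identify them. The discarded eyes carry part of that information. If the rule compresses the response that biomechanics might explain, a real association is estimated as too weak and may be missed. An association with baseline sphere, if examined, can move the other way.

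**Working it through.** **Inputs from the documents.** The eye rule and its tie-breaks; the outcome; baseline sphere of -4.00 to -5.00 D; fellow eyes within 1 D of each other. There is no stated sample size, power or effect size to reproduce.

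**Step 1: an identity that needs no assumption.** Write B for baseline myopia, M for residual myopia (positive if under-corrected) and D for reduction. Then D = B - M, so |D - B| = |M|. Ties aside, the rule keeps the eye whose reduction lies closest to its own baseline sphere.

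That need not be the eye with the larger reduction. Suppose one eye goes from -5.00 to -0.50 D (reduction 5.00 - 0.50 = 4.50 D) and its fellow from -4.00 to -0.25 D (4.00 - 0.25 = 3.75 D). The plan analyses the second eye.

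**Step 2: biomechanical predictor with a real effect (simulation).** All of the following are assumptions:
- normal residuals with SD 0.35 or 0.50 D, rounded to 0.25 D;
- inter-eye noise correlation 0.4 to 0.8;
- inter-eye correlation of baseline sphere 0.6 or 0.9;
- inter-eye correlation of the predictor 0.8 to 1.0.

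The full rule was applied to about 400,000 simulated subjects per scenario and compared with the right eye, for which r was about 0.40. Sample size for 80% power at two-sided 5% is n = [(1.960 + 0.842) / atanh(r)]² + 3. With rounding, the fixed-eye r is about 0.395, giving (2.802 / 0.4177)² + 3 = 48. At r = 0.34, (2.802 / 0.3541)² + 3 = 65.6, or 66. The tabled n values use unrounded correlations.

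| Mean residual | r, plan's rule | n for 80% power (right eye: about 48) | Slope as multiple of right-eye slope |
|---|---|---|---|
| plano | 0.28-0.37 | 56-100 | 0.58-0.83 |
| -0.25 or +0.25 D | 0.31-0.38 | 54-82 | 0.63-0.87 |
| -0.50 D | 0.34-0.39 | 51-66 | 0.75-0.95 |
| -0.75 D | 0.36-0.41 | 46-58 | 0.86-0.99 |

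At -1.00 D the multiplier is about 0.9 to 1.0. If the predictor's inter-eye correlation may lie anywhere from 0 to 1, the multiplier spans 0.19-0.83 at plano and 0.61-0.99 at -0.75 D.

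A different set of assumptions gives the same pattern (residual SD 0.5 D, predictor explaining 25% of residual variance, predictor inter-eye correlation 0.5 or 0.9). The slope multiplier is 0.45-0.78 at plano, 0.66-0.86 at -0.50 D and 0.85-0.95 at -1.00 D. With an assumed 30 subjects, noise correlation 0.6 and predictor correlation 0.9, power goes from 69% to 52% at plano, from 69% to 61% at -0.50 D, and stays at 68% at -1.00 D.

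**Step 3: the direction is not guaranteed.** Suppose each eye ends at plano with probability 0.15 and otherwise at -1.00 D. The SD for one eye is √(0.15 × 0.85) = 0.36 D. If the eyes were independent, the selected eye would be at plano with probability 1 - 0.85² = 0.2775, giving SD √(0.2775 × 0.7225) = 0.45 D, which is larger. With a predictor shared by both eyes, simulation gave SD 0.42-0.44 D, and r rose from 0.26 to 0.30-0.34.

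**Step 4: baseline sphere as predictor.** With normal noise, a true slope of 0.60 becomes 0.72-0.81 at plano and 0.63-0.70 at -0.75 D. The correlation rises from 0.39-0.51 to 0.54-0.75 and 0.44-0.58 respectively. A true slope of 1 is unchanged, although r still rises.

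**Step 5: predictor unrelated to residual and baseline sphere.** With equal response spread, |r| stays below 0.005. In a separate run with an assumed 30 subjects, type I error was 5.0-5.2% under either eye rule. If response SD changes by 20% per predictor SD, a false r of 0.02-0.09 appears at -0.75 D, and about 0 at plano.

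**Step 6: mean reduction.** The rule shifts it by +0.02 to +0.22 D at mean residuals of -0.25 to -0.75 D, by 0 at plano, and by -0.02 to -0.11 D at +0.25 D.

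**The case against.** The rule is written down, deterministic and keeps one eye per subject, so it leaves no room for ad hoc choice and creates no clustering. Objective 1 concerns successful orthokeratology, for which taking the better corrected eye is arguable. A predictor with no relation to response keeps its type I error. If eyes end 0.75 to 1.00 D under-corrected on average, a biomechanical correlation hardly changes. Every size above is assumed, and they run from severe to negligible.

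Most of this stands. It does not answer the central point, because a written rule prevents ad hoc choice but not selection on the outcome.

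Three stronger readings are tempting, and the documents do not support them:
- **That the rule must trim response variation, and so must attenuate.** The identity in step 1 does not imply this. A smaller absolute residual can come with a wider spread, as step 3 shows.
- **That the rule pushes baseline refraction ahead of biomechanics as best predictor.** The plan does not list baseline sphere as a predictor, and Objective 2 does not ask whether biomechanics outranks it. A large swing in ranking appears only if the two are assumed equally strong. With a baseline slope of 1 and 30 subjects, baseline sphere already ranks first in 88-99% of simulated studies using the right eye, against 90-100% under the plan's rule.
- **That Objective 1 is biased.** Nothing here shows bias in biomechanical change over time.

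**Conclusion.** The concern holds for Objective 2, in conditional form. The plan selects the analysed eye on a component of the outcome it then models, and offers no analysis free of that selection.

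With roughly normal residuals, the slope of a biomechanical predictor with a real effect is usually attenuated: most near plano, still noticeably at -0.50 D, and little at -0.75 to -1.00 D. Skewed residuals can reverse this. If baseline sphere is examined, its association tends to be strengthened.

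A reader might infer widespread false positives or a uniformly flattered mean reduction. Neither follows. A predictor unrelated to residual and baseline sphere is essentially unbiased when spread is equal, and the mean shifts down if eyes are over-corrected on average. For biomechanics the main risk is a weakened slope and lost power.

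That the rule selects on the outcome is certain from the text. The size is not, because residual mean, SD, inter-eye correlations and sample size are all undocumented.

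**What to change.** Change the eye for the prediction analysis only. Suggested wording:

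*For the regression of 6-month sphere reduction on baseline parameters, the right eye of each 6-month completer is analysed. Results for the eye whose residual sphere is closer to plano are reported as a labelled sensitivity analysis.*

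The right eye is already the plan's last tie-break. In the simulations it recovered the true slopes. The eye rule for Objective 1 may stay as it is.

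The methods are written in the past tense. If 6-month data have already been seen, report both analyses and label the right-eye analysis post hoc.

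**Cost.** No new data are needed, because the current rule already requires both eyes at 6 months, and one eye per subject is kept. The reported reduction may be slightly less favourable if eyes were under-corrected on average (up to about 0.2 D under the assumptions above). Different eyes may then serve the two objectives, which the report should state.

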Corneal Biomechanics and Corneal Reshaping Therapy NCT02719535 March 25 2016

(a) Introduction

Myopia is highly prevalent in Asian populations, especially Chinese populations [1], and now affects Americans and Europeans as well.[2-3] Low to moderate myopia is not a major concern, but high myopia (more than 6D) is associated with retinopathy and glaucoma and is an economic burden on society.[4]

Various treatment options have been proposed to reduce the progression of myopia, including the use of pharmaceutical agents and different types of corrective lenses. [5-8] Corneal reshaping, also called orthokeratology, is an intervention with proven efficacy in retarding myopia progression. [10]

In orthokeratology, the corneal curvature is altered after a patient wears the lenses. The effective treatment range is usually not more than 5D of myopia and not more than 1.5D of astigmatism. In addition, orthokeratology can be slow or ineffective in some patients. This may be related to the pre-treatment corneal parameters such as the apical radius and eccentricity.[11] Corneal biomechanical properties may also be a factor, but accurate measurement of the influence is difficult.

Most interventions for myopia control begin in early childhood. After commencement of the treatment, several years of continual monitoring is required to confirm its efficacy. If the intervention is eventually ineffective, then the time would have been wasted. The goal of the proposed study is to investigate whether corneal biomechanics are predictive of successful orthokeratology. If pre-treatment corneal biomechanics combined with other conventional corneal parameters do not indicate successful orthokeratology, patients can be advised to try other more effective interventions earlier.

(b) Objectives

- 1. To monitor the changes of corneal biomechanics from long-term (6 months) successful orthokeratology
- 2. To determine if corneal biomechanics is predictive of the rate of orthokeratology

(c) Methods

Subjects

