After all non-contact procedures, the cornea was anesthetized using one drop of 0.4% benoxinate. Intraocular pressure was measured using Goldmann applanation tonometry (GAT) followed by corneal biomechanics by using a corneal indentation device. Two GAT readings were taken and the mean result was used for analysis. The indenter first touched the central cornea. After the pre-load was stabilized (through an audible sound), the indenter moved forwards and backwards at 12mm/s to indent the cornea by 1mm. The indentation was completed in less than 0.25 seconds. The corneal stiffness was read from the device and the tangent modulus was calculated from the corneal radius of curvature and central thickness. Three corneal indentations were obtained, and the average was used for analysis.

Lenses used

After the suitability for wearing corneal reshaping lenses was confirmed through slit-lamp biomicroscopy, subjects were fitted with orthokeratology lenses. The lenses used were reverse geometry lenses (Menicon Z Night contact lens) made of super high gas permeable material (Menicon Z, DK 163 ISO). Lens fitting was based on the manufacturer's instructions (Easy Fit Software, Menicon Co Ltd., Nagoya, Japan) according to ocular information, including corneal topography, non-cycloplegic manifest refraction, and horizontal visible lens diameter. Lens fitting was assessed with fluorescein. An optimal fluorescein pattern consisted of 3 to 4mm of central touch, 1 to 1.5mm of mid-peripheral pooling and 1 to 1.5mm of peripheral alignment. A bull's eye fluorescein pattern was considered an optimum fit.

Wearing schedule

After a successful trial fit, a delivery visit was arranged. The subjects were returned to the clinic after an overnight lens wear. The same fluorescein pattern was maintained after overnight orthokeratology. The subjects were the lenses every night and they were required to return regularly. Further follow-up visits were taken place after the first week, 1 month, 3 months and 6 months of lens wear. Each visit was within two hours after waking up in the morning and the lenses being removed.

In addition to corneal topography, corneal thickness, and corneal biomechanics measurements (using both ORA and corneal indentation device), subjective refraction and ocular biometry were included in all follow-up visits. Both the habitual and best-corrected visual acuities were measured.

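### Baseline predictors are searched for and judged on the same completers, with no validation or multiplicity control, so apparent predictive strength will be optimistic, severely so if the unstated sample is small

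*Combined protocol and SAP*

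**What the plan says.** Objective 2 asks whether corneal biomechanics predicts the rate of orthokeratology. The analysis serving it is in (c) Methods, Analysis of data: "Baseline ocular parameters that could best predict myopia reduction were identified through linear regression (Pearson or Spearman"). The outcome is given as "Reduction of sphere at the 6-month visit was used as the dependent outcome response", and "the various baseline ocular parameters were treated as independent predictors".

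The candidates are not listed there, but Procedures names the baseline measurements: "The following baseline data were collected: non-cycloplegic manifest refraction, ocular biometry through partial coherence interferometry", then topography and corneal thickness. From the ORA, "Corneal hysteresis (CH), corneal resistance factor (CRF), and corneal-compensated intraocular pressure (IOPcc) were measured". For tonometry, "Two GAT readings were taken and the mean result was used for analysis". From the indentation device, "The corneal stiffness was read from the device and the tangent modulus was calculated from the corneal radius of curvature and central thickness".

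The analysis set is one eye of each subject who completed six months. The document states no sample size, primary predictor, rule for what counts as best, significance level, multiplicity adjustment or internal or external validation. The Introduction gives the motive: if the baseline parameters do not indicate success, "patients can be advised to try other more effective interventions earlier".

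**The concern.** Searching several candidates for those that predict best, then reading predictive strength off the same data, favours whichever candidates chance has flattered. The fit of the selected parameters is biased upward, and unadjusted testing of many candidates makes a spurious finding likely when none has any value.

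This is the only analysis described for Objective 2. An uncorrected R-squared does not tell the reader how well the selected parameters would do in new patients, which is what matters if baseline measurements are ever to inform a choice of treatment.

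**Working it through.** The plan states no figure for sample size, power or predictive strength, so there is nothing to reproduce. The check asks how large the optimism could be.

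**Number of candidates (k).** From Procedures: sphere, cylinder, axial length, keratometry, thickness (5); CH, CRF, IOPcc (3); GAT (1); stiffness and tangent modulus (2). Total 5 + 3 + 1 + 2 = 11, or 12 if steep and flat keratometry count separately.

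**Assumptions not in the documents.** Two-sided 0.05 per candidate; n from 20 to 200; normal data; equal correlation between candidates of 0, 0.3 or 0.5; one true predictor with r = 0, 0.3 or 0.5; the candidate with the largest |r| is selected.

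**Chance of a false predictor when nothing predicts.** For independent candidates it is 1 - 0.95^k:
- k = 11: 1 - 0.95^11 = 43.1%
- k = 12: 1 - 0.95^12 = 46.0% (46 to 47% by simulation)
- wider range: 33.7% for k = 8, 51.2% for k = 14

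With 11 candidates the simulated chance is about 37 to 40% at inter-correlation 0.3 and about 31% at 0.5. It does not fall with n: at inter-correlation 0.3 it is 37.2%, 39.5%, 37.8%, 38.0% and 39.1% at n = 20, 30, 50, 100 and 200.

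**Optimism in R-squared.** The selected predictor's apparent R-squared was compared with its R-squared in new subjects and with a bootstrap-corrected value. The correction is: corrected = apparent - mean over resamples of (R-squared in the resample - R-squared of that resample's model in the original data), with selection repeated in every resample. A negative out-of-sample value means the model predicts worse than the outcome mean. Results for k = 11, inter-correlation 0.3, true r = 0.3:

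| n | Apparent | True out-of-sample | Bootstrap-corrected |
|---|---|---|---|
| 20 | 0.23 | -0.21 | -0.12 |
| 30 | 0.17 | -0.09 | -0.07 |
| 50 | 0.13 | -0.01 | -0.01 |
| 100 | 0.11 | 0.06 | 0.04 |

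Separate runs differ by about 0.01 to 0.02. The gap (apparent minus true) is 0.44, 0.26, 0.14 and 0.05. The true predictor is the one selected 29%, 38%, 55% and 80% of the time.

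With true r = 0.5 the apparent and true values are 0.31 and 0.01 at n = 20, 0.28 and 0.12 at n = 30, 0.26 and 0.20 at n = 50, and 0.26 and 0.23 at n = 100.

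**Limit of the correction.** At n = 20 with 12 uncorrelated candidates and no true predictor, the corrected value is -0.17 against a true -0.31. It moves the right way but stops short.

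**Price of multiplicity control.** With Bonferroni over 11 candidates (0.05/11), the critical |r| = t / sqrt(n - 2 + t²) rises from 0.361 to 0.504 at n = 30 and from 0.197 to 0.282 at n = 100. By Fisher's z, the n for 80% power rises from 85 to 145 for r = 0.3 and from 30 to 48 for r = 0.5.

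**The case against.** - **Sample size.** A reader might infer that the reported strength is bound to be badly inflated. The documents do not support that, because n is not given. At n = 100 with r = 0.5 the gap is about 0.03, and at n = 200 with r = 0.3 the mean selected |r| is 0.30 against a true 0.29. This part of the objection stands. The direction of the bias is established; its severity is conditional.
- **Correlated candidates.** Tangent modulus is calculated from radius and thickness, and CH, CRF and IOPcc come from the same instrument, so treating candidates as unrelated overstates the false-positive chance. This also stands, and it is why the range runs down to 31%. Correlation lowers the chance but does not remove it.
- **Selection rule.** The plan speaks of parameters in the plural and never says that one winner is picked by the size of r, or which strength measure is reported. Pick-the-largest is a model of the plan. But an unstated rule leaves the choice open after the data are seen, which does not reduce the optimism.
- **Patient advice.** A reader might infer that the study will steer patients by its result. The Introduction offers this only as a prospective use, for biomechanics combined with conventional parameters, and issues no decision rule.
- **The remedy.** One might want to call a parameter predictive when the corrected R-squared exceeds zero. That rule is unsound. The corrected value describes the whole selection procedure, not one parameter. The rule passes about 5 to 13% of null data sets, and it is met only about a quarter of the time at r = 0.3 and n = 30.

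**Conclusion.** The concern holds in a conditional form. As written, the plan selects and judges predictors on the same completers, from about 11 to 12 candidates, without validation or multiplicity control. The apparent predictive strength for Objective 2 will be optimistic: severely so at n of about 20 to 50 with a weak or null signal, and little at n of 100 or more with a moderate one. Separately, if nothing predicts, the chance of at least one p<0.05 is about 31 to 47% for 11 to 12 candidates with inter-correlation between 0 and 0.5, whatever the sample size.

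The figures rest on the assumed n, normal data, equal inter-correlation, a single true predictor and selection by the largest |r|. None of these is in the documents. The conclusion that correction is needed does not depend on knowing n: where the gap is material the bootstrap moves the estimate towards the truth, and where the gap is small it changes little.

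**What to change.** Add to Analysis of data:

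- List the candidate parameters and state the selection rule.
- Repeat the full predictor-selection procedure in each of at least 500 bootstrap resamples of subjects.
- Beside the apparent values, report the optimism-corrected R-squared and prediction error in dioptres for the whole procedure, with the frequency at which each parameter is selected.
- Base statements about predictive strength on the corrected values, noting that the correction is incomplete at about n = 20.
- Do not use a corrected R-squared above zero as a test of an individual parameter. If single parameters are tested, report p-values adjusted for multiplicity across all candidates.

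**Cost.** A few lines of code, possibly outside SigmaPlot, and no new subjects or measurements. The reported R-squared will be less favourable, and adjusted tests of single parameters lose power.

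### Objective 2 asks whether corneal biomechanics predict the result of orthokeratology, but the planned regression commits to no measure of prediction error

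*Combined protocol and SAP*

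**What the plan says.** Section (a), Introduction, sets the aim: "The goal of the proposed study is to investigate whether corneal biomechanics are predictive of successful orthokeratology". It then gives the use, which is that "patients can be advised to try other more effective interventions earlier". The condition attached to that advice is worded as follows: "If pre-treatment corneal biomechanics combined with other conventional corneal parameters do not indicate successful orthokeratology". Section (b), Objectives, makes this Objective 2: "To determine if corneal biomechanics is predictive of the rate of orthokeratology".

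The analysis is in section (c) Methods, under Analysis of data: "Baseline ocular parameters that could best predict myopia reduction were identified through linear regression (Pearson or Spearman"). The outcome is continuous: "Reduction of sphere at the 6-month visit was used as the dependent outcome response". On the other side of the equation, "the various baseline ocular parameters were treated as independent predictors". The analysis set is described only as "Data of one eye of each subject who completed the 6-month orthokeratology were analyzed", with no number.

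For Objective 2 the section names no slope with an interval, R-squared, residual SD, prediction interval or validation. It defines neither a successful result nor the size of relation that would count as predictive. It also states no test and no alpha for this objective.

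**The concern.** Advice to a patient before treatment depends on how far the predicted sphere reduction is likely to lie from the one that patient obtains. A correlation coefficient describes how two quantities move together across a group; it does not give that distance in dioptres. A Spearman coefficient works on ranks and yields no predicted dioptre value at all. This would be true even if the coefficient were known without error, so a larger sample or control of multiple testing would not cure it.

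The risk is one of labelling. With nothing fixed beforehand, a parameter with a modest association could be reported as predictive, and the finding carried towards patient advice, although knowing the parameter barely changes the expected result.

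**Working it through.** The documents give no figure to reproduce: no n, alpha, power, target r or outcome SD. The check therefore asks how much scatter a just-significant correlation would leave.

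**Assumed inputs:** two-sided 5% level; a single linear predictor; n = 20 to 60 completers, one eye each (10 and 100 as a wider check).

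**Formulas**
- Critical r = t / √(t² + n − 2), with t the 0.975 quantile on n − 2 df.
- Residual SD as a share of outcome SD = √(1 − r²); unexplained variance = 1 − r².
- The same SD share corrected for the fitted slope = √[(1 − r²)(n − 1)/(n − 2)].
- Upper 95% limit for a true r, by Fisher z = tanh[atanh(r) + 1.96/√(n − 3)].

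**Example, n = 30:** r = 2.048/√(2.048² + 28) = 2.048/5.674 = 0.361. Residual SD share = √(1 − 0.130) = 0.933. Upper limit = tanh(0.378 + 1.96/√27) = tanh(0.378 + 0.377) = 0.638.

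| n | t | Critical r | Residual SD | Unexplained variance | Residual SD, df-corrected | Upper 95% limit if r just misses |
|---|---|---|---|---|---|---|
| 20 | 2.101 | 0.444 | 89.6% | 80.3% | 92.1% | 0.741 |
| 30 | 2.048 | 0.361 | 93.3% | 87.0% | 94.9% | 0.638 |
| 40 | 2.024 | 0.312 | 95.0% | 90.3% | 96.2% | 0.568 |
| 60 | 2.002 | 0.254 | 96.7% | 93.5% | 97.5% | 0.477 |

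At n = 10 the residual SD share is 77.5%, and at n = 100 it is 98.0%.

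**What r would be needed.** Solving √(1 − r²) for r: a 10% cut in SD needs r = 0.44, a 20% cut 0.60, a 30% cut 0.71 and a 50% cut 0.87. Significance arrives well before these larger cuts, and earlier still as n grows.

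**In dioptres.** With an assumed outcome SD of 0.4 D, the 95% half-width for one patient is 1.96 × 0.4 = 0.78 D without the predictor and 0.78 × 0.933 = 0.73 D at r = 0.361. Halving the assumed SD gives 0.39 D and 0.37 D; doubling it gives 1.57 D and 1.46 D. The proportional narrowing, about 7%, does not depend on the SD.

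**Non-significant results.** An r just short of significance leaves true values up to 0.74 (n = 20), 0.64 (n = 30) or 0.48 (n = 60) open, which would leave 67%, 77% or 88% of the SD. An observed r of about zero has limits of ±0.44, ±0.36 and ±0.25, and so excludes a single linear predictor that cuts the SD by more than about 10%, 7% and 3%. The two cases mean different things, and only an interval separates them.

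**The case against.** The strongest reply is that the section says linear regression, with a dependent outcome and independent predictors. Such a fit produces a slope in dioptres, R-squared and a residual SD, so *Pearson or Spearman* may be no more than loose labelling. That is fair, and it is why the remedy is cheap. But the plan does not commit to reporting these quantities or to judging Objective 2 by them.

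A reader might go further and infer that Objective 2 is settled by a significance test. The documents do not support this: they state no test or alpha for it. The just-significant r is used here only as a benchmark for how weak a relation could be and still attract the word predictive.

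A second objection is that the Introduction speaks of biomechanics together with conventional corneal parameters, while the figures above are for one predictor. This stands. A combined model could leave less scatter, and the section does not say whether one is fitted. The fix therefore covers it.

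A third is that the advice sentence is motivation, not a promise of a decision tool, and that association is a usual first step in exploratory work. This also stands in part. It supports reporting an association as an association; it does not support calling it prediction without a measure of error.

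**Conclusion.** The point holds as a gap between the question and the committed analysis. Under the stated assumptions (20 to 60 completers, two-sided 5%, one predictor), a just-significant r of 0.44 to 0.25 leaves 90-97% of the outcome SD, or 80-94% of its variance. The percentages depend on the assumed n and are not figures from the documents. The change should be made, but the data already collected can answer the question; the defect lies in what is reported.

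Two stronger readings should be avoided.

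- *A non-significant r rules out little.* This is too broad. It is fair for a just-missed r at about n = 20 to 30, but an r near zero excludes all but weak linear prediction. By the Fisher z approximation, power for a true r of 0.5 is 62% at n = 20, 81% at n = 30 and 99% at n = 60.
- *A fixed cut-off separates predictive from not predictive.* The documents contain none. A 25% cut in error, for instance, would need r = √(1 − 0.75²) = 0.66. A rule built on it can contradict itself: at n = 30 a significant r of 0.361 has an upper limit of 0.638, so it would be both associated and not predictive. Any threshold is for the sponsor to choose and justify beforehand.

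**What to change.** In Analysis of data, for each biomechanical predictor and for the model combining biomechanics with conventional corneal parameters, state that the report will give:

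1. the slope in dioptres of sphere reduction per unit of the predictor, with its 95% CI;
2. the leave-one-out prediction error SD in dioptres for three models side by side: intercept only, conventional corneal parameters alone, and those parameters with biomechanics added;
3. the 95% CI for r or R-squared, and a 95% prediction interval for sphere reduction at a low and a high value of the predictor.

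Add two rules of wording. A parameter is called predictive only to the extent that it lowers the leave-one-out error, with the reduction quoted; otherwise it is called associated. A non-significant r is interpreted through its CI. If the sponsor wants a size threshold, it should be set and justified before the analysis. Spearman can stay as a description of association, but the prediction measures must come from a fitted model.

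The cost is some SAP wording and a few more lines of output, with no new patients, visits or measurements. The downside is that the reported strength of prediction will probably look less favourable.
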